Effects of Late-evening Snacks on Nutritional Status and Metabolic Pattern of Patients With Primary Hepatocellular Carcinoma After Hepatectomy

Source: Drum Tower Hospital, Medical School of Nanjing University

Subject No.: None

Person in charge: [name], [name]

Department: Pharmacy

Contact: [name], [name]

[contact], [name]

Study start date: February 2024

Version number: V2.0

Version date: December 22, 2023

Produced by Drum Tower Hospital, Medical School of Nanjing University

Formula Case Abstract Summary

Project name	Effects of Late-evening Snacks on Nutritional Status and Metabolic Pattern of Patients with Primary Hepatocellular Carcinoma After Hepatectomy
Research purpose	To observe the effects of Late-evening Snacks on the nutritional status, liver function recovery, complication rate and long-term prognosis of hepatocellular carcinoma patients who underwent hepatectomy, and to further explore the effects of Late-evening Snacks on the metabolic pattern of the patients, and to identify the serum differential metabolites, in order to initially investigate the potential mechanism of Late-evening Snacks to improve the nutritional status of the patients, and to provide theoretical basis for the development of an effective nutritional regimen in the clinic.
Research design	Single-center prospective cohort study
Total Number of Cases	106 cases
Case selection	
Inclusion Criteria:
 
 1. Age 18-75 years; 2. Meet the diagnostic criteria of China's "Guidelines for Diagnosis and Treatment of Primary Liver Cancer (2022 Edition)", clinically diagnosed with primary liver cancer, hospitalized with radical hepatectomy as the main surgical treatment, no indication of metastasis of the tumor to extra-hepatic organs in preoperative tests and examinations, no absolute contraindications to surgery, complete resection of the liver tumor in the operation, and hepatocellular carcinoma confirmed by postoperative pathological diagnosis; 3. Child-Pugh grades A and B; 4. Preoperative Eastern Cooperative Oncology Group Physical Status Score

	
(ECOG-PS) of 0 to 2;
 
5. The patient is conscious, has normal verbal communication, and is able to cooperate with the relevant examinations;
 
6. Fully informed about the study and voluntarily signed an informed consent form.

	
Exclusion Criteria:
 
1. Failure to meet selection criteria;2. Nutritional assessment as cachexia;3. Presence of contraindications to enteral nutrition (EN) or EN intolerance, such as acute gastrointestinal bleeding, intestinal obstruction. (\geq grade 3, National Cancer Institute-Common Terminology Criteria for Adverse Events [NCINCI-CTCAE v 5.0]);4. Simultaneous combination of malignant tumors in other parts of the body;5. Combined hepatic encephalopathy or definite infection on admission;6. Known refractory metabolic diseases (e.g., poorly controlled diabetes mellitus or fasting glucose \geq10 mmol/L, hyperthyroidism, hypothyroidism, metabolic acidosis);7. Decreased renal function (defined as serum creatinine Cr level \geq176.8 μmol/L);8. Intravenous or oral nutritional supplements, such as proteins, amino acids, etc., applied within one month prior to admission to the hospital;9. Patients with severe stress or severe complications such as respiratory failure with severe cardiac, hepatic, renal and other insufficiencies;10. Persons with mental and neurological disorders who are unable to cooperate with a physician;11. Alzheimer's disease, cerebral atrophy, acute stage or sequelae of cerebrovascular disease, cognitive impairment;12. Previously poor adherence to medication and nutritional counseling;13. Critically ill and difficult to assess;

	
14. On the liver transplant waiting list or under consideration for liver transplantation, as such patients may discontinue follow-up before the end of the study;
 
15. Less than 12 months since last localized treatment (TACE or HAIC or ablative therapy);
 
16. Other circumstances that the researcher considers inappropriate for participation in the study.

Treatment plan	
Patients who were admitted to the Department of Hepatobiliary Pancreatic Surgery of Drum Tower Hospital affiliated to Nanjing University School of Medicine from February 2024 to January 2025 were selected and screened for enrollment according to the admission criteria. The grouping was not randomized and blinded, and all patients were enrolled according to their individual wishes and divided into a test group (53 cases) and a control group (53 cases). The purpose of the study, the content of the investigation were explained to the patients or their families at the time of admission, the principle of confidentiality was informed to reduce the concerns of the respondents, and the subjects were included in the study after signing an informed consent form after obtaining their consent.
 
1. Treatment programs
 
All patients were screened for nutritional risk within 24h of admission using NRS 2002, nutritional assessment using PG-SGA, and malnutrition diagnosis using GLIM malnutrition assessment (diagnosis) criteria. A target daily amount of 25-30 kcal/kg was set for the patients. Nutritional management was standardized to ensure a balanced dietary intake in both groups. Nutritional cards were issued to each patient according to his/her intake, and were explained and emphasized at the time of admission and at the time of discharge. Patients were asked to choose different food items on the cards according to their own food preferences and actual situation. The experimental group was required to have late-evening snacks (LES) within

	
1hour before bedtime, while the control group did not have any food during the 1hour before bedtime.
 
Test group: patients will have an additional meal (total calories 200-275kcal, protein 11.5g-18g, complex carbohydrates 25-55g) 1h before bedtime. The dietary regimen of the test group will be subtracted from the corresponding late-evening snacks intake.
 
(1) Preoperative: ①Patients without nutritional risk: independent intake according to the issued diet program card. ②Patients with nutritional risk: daily oral whole-protein enteral nutrition on the basis of general diet after admission.
 
(2) Postoperative: start drinking small amount of water on the 1st postoperative day, after ventilation, over to liquid diet, and on the 2nd postoperative day, it can be over to autonomous semi-fluid diet + daytime oral enteral nutrition of whole protein type + LES regimen. As the patient's voluntary intake meets 60% of the body's needs, the daytime oral enteral nutrition support can be gradually stopped and the LES regimen can be continued.
 
3) Discharge: daily intake is required on time according to the LES regimen.
 
Control group: no more food 1h before bedtime.
 
(1) Preoperative: same as the test group.
 
(2) Postoperative: start drinking small amount of water on the 1st postoperative day, after ventilation, over to liquid diet, and on the 2nd postoperative day, it can be over to autonomous semi-fluid diet + daytime oral enteral nutrition of whole protein type. As the patient's voluntary intake meets 60% of the body's needs, the daytime oral enteral nutrition support can be gradually stopped and the LES regimen can be continued.
 
(3) Discharge: the doctor will judge whether the patient needs to continue nutritional support according to his/her dietary recovery, and if so,

--	---

	
his/her supplementation must be completed before 1h before bedtime.
 
2. Biological sample collection:
 
The remaining post-test serum samples need to be collected for metabolomics analysis from patients on day 1 of admission, postoperative day 6, postoperative 1 month, postoperative 3 months, and postoperative 6 months.
 
3. Clinical data collection:
 
1) General information: gender, age, height, weight, BMI, ICG 15min retention time, name of surgery, duration of surgery, blood loss, blood transfusion, tumor stage, NRS2002, GLIM malnutrition assessment (diagnostic) criteria diagnosis.
 
2) Nutritional indicators: Nutritional indicators such as serum albumin (ALB), prealbumin (PA), transferrin (TRF), and total serum protein (TP) were collected from patients on the 1st day of admission, the 6th postoperative day, 1 month postoperatively, 3 months postoperatively, and 6 months postoperatively.
 
(3) Liver function indexes: Liver function indexes such as alanine aminotransferase(ALT), alanine transaminase(AST), γ-glutamyltransferase (GGT), cholinesterase (CHE), and total bilirubin (TBIL) were collected on the 1st day of admission, the 6th postoperative day, 1 month postoperatively, 3 months postoperatively, and 6 months postoperatively.
 
(4) Clinical outcome: collect the patients' postoperative clinical outcome indicators, such as: postoperative complication rate, recurrence-free survival, and quality of survival.
 
(5) Medical costs: collect the total cost of the patients' hospitalization, the cost of anti-infective drugs, and the cost of albumin during hospitalization.

Evaluation of the	
Indicators of effectiveness evaluation
 
Main efficacy indicators: serum albumin (ALB)
 
Secondary efficacy indicators: serum prealbumin (PA), alanine

efficacy of treatment	aminotransferase (ALT), azelaic transaminase (AST), cholinesterase (CHE), total bilirubin (TBIL), total hospitalization costs, relapse-free survival, and quality of life
	
Safety evaluation indicators
 
Incidence of gastrointestinal symptoms such as abdominal distension, diarrhea, nausea and vomiting, incidence of postoperative complications, and length of postoperative hospitalization

Statistical methods	
Descriptive statistics were performed on the clinical data, and measures that conformed to normal distribution were expressed as mean±standard deviation ($\bar{x} \pm s$), and t-test was used between groups, and measures that did not conform to normal distribution were expressed as median (interquartile spacing) [M(IQR)], and Mann-Whitney U test was used between groups. Count data were expressed as percentages [n(%)], and the chi-square test was used for between-group comparisons, with $P<0.05$ considered statistically significant. The Kaplan-Meier method in STATA 12.0 was used to calculate the recurrence rate and recurrence-free survival in each group, and the log-rank test was used for intergroup comparison.

Duration of the study	24 months

catalogs

1. Research background	1
2. Research purpose	4
3. Types of Research Designs and Experimental Steps	4
4. Case selection	9
5. Research Methodology and Technical Approach.....	10
6. Observed items and testing time points	12
7. Criteria for evaluating the efficacy of treatment	13
8. Adverse Events Watch.....	14
9. Data security monitoring.....	16
10. Statistical processing	16
11. Ethical principles of clinical research.....	17
12. Reference	17

1. Research background

Primary liver cancer (hereinafter referred to as hepatocellular carcinoma) is one of the common malignant tumors of the digestive system worldwide, which can be classified into hepatocellular carcinoma (HCC), intrahepatic cholangiocarcinoma (ICC), and combined hepatocellular-cholangiocarcinoma (cHCC-CCA) according to the different pathologic types. According to the Global Tumor Epidemiology Statistics 2020 (GLOBOCAN), the number of newly diagnosed cases of hepatocellular carcinoma amounted to 906,000, which is the 6th most common type of cancer, and the number of deaths amounted to 830,000, which is the 3rd most common type of cancer ^[1]. And the incidence rate of liver cancer in China is located in the 4th place, the mortality rate is located in the 2nd place ^[2], and the 5-year survival rate is 14.1% ^[3]. The treatments for hepatocellular carcinoma vary according to the stage and liver function level, including hepatic resection, liver transplantation, ablation therapy, transarterial embolization, radiation therapy, etc. Among them, hepatic resection is considered to be the most effective treatment for early-stage hepatocellular carcinoma and is the main treatment at present, with a 5-year survival rate of up to 69.0%~86.2% ^[4]. Research results show that the local recurrence rate of selecting surgical resection treatment modality is significantly lower than that of radiofrequency ablation for hepatocellular carcinoma patients with good liver function reserve, and the long-term efficacy is better ^[5,6].

At the same time, the liver serves as the target organ for the metabolism of most nutrients, and the high metabolic status and organ invasion of cancer often expose liver cancer patients to malnutrition, with an incidence rate as high as 74.36% according to a survey ^[7]. In addition, hepatic resection will cause hepatocyte damage to a certain extent, resulting in the metabolic balance of sugar, protein, fat and hormones in the patient's body being disrupted, which makes the body's catabolism stronger than anabolism ^[8], and it is more likely to have a decrease in the level of albumin synthesis and a significant decrease in the intake of nutrients after the operation, which in turn results in the decrease in the patient's ability to resist infection, the increase in the risk of complications, and the decrease in the quality of life and a series of other poor prognosis ^[9,10,11,12], therefore, nutritional support and intervention are particularly important in this situation. According to our previous study, we found that nutritional intervention by clinical pharmacists in perioperative liver cancer hepatectomy patients could reduce the complication rate by 69%, as well as correct the inflammatory stress response and improve albumin levels more quickly ^[13].

Therefore, we believe that the use of rational and effective nutritional intervention strategies will bring positive benefits to patients.

The 2022 Guidelines for Perioperative Care in Liver Surgery: the Accelerated Rehabilitation After Surgery Society (ERAS) recommends early intake after hepatic resection and oral nutritional supplements for malnourished patients ^[14]. However, for patients with abnormal liver function or cirrhosis their perioperative and postoperative nutritional support and nutritional support patterns lack guideline recommendations. Abnormal liver function and inadequate intake in postoperative patients cause patients to exhibit reduced hepatic glycogen reserves, enhanced gluconeogenesis and fat oxidation, and increased protein oxidative catabolism. To mitigate accelerated starvation and associated protein hydrolysis, the most critical dietary strategy is to eat meals every 4 to 6 hours with the shortest possible interval between meals. Therefore, the concept of Late evening snack (LES), in which a portion of food is moved to bedtime while the total daily intake remains unchanged, has been proposed to effectively improve the metabolic state of accelerated catabolism and has been recommended by the European Society of Clinical Nutrition and Metabolism (ESPEN) for patients with cirrhosis who have a high catabolic metabolism^[15], without indicating the specific nutritional composition, while the International Society for Hepatic Encephalopathy and Nitrogen Metabolism recommended in its consensus published in 2013^[16] that LES should contain at least 50 g of complex carbohydrates. In most studies, various combinations of LES (200-275 kcal total calories, 11.5g-18g protein, and 25-55g complex carbohydrates) have been shown to be significant in improving liver function indices and nutritional indices ^[17]. Researchers have suggested that LES containing complex carbohydrates and proteins may reduce lipid oxidation and improve nutritional status, muscle mass, liver function and quality of life in patients ^[18,19].

The results of a study in an outpatient long-term late-evening snacks also confirmed a significant improvement in nitrogen balance compared to baseline and an increase in serum albumin levels ^[20]. In a meta-analysis published in 2018 ^[19], serum albumin, prealbumin, and cholinesterase levels were significantly elevated in patients with cirrhosis after implementation of LES. In addition, Chen et al ^[17] found that LES reduced the levels of alanine aminotransferase (ALT), alanine aminotransferase (AST), prothrombin time (PT), and blood ammonia in patients with liver disease, and reduced the incidence of ascites. With further research, Takeshita et al ^[21] found that LES prevented the decline of albumin levels in hepatocellular carcinoma patients undergoing chemoembolization therapy (TACE) and reduced hepatic impairment due to TACE. Meanwhile, Harima et al ^[22] showed that LES improved prealbumin levels,

BCAA/tyrosine, and ALT in patients with advanced hepatocellular carcinoma treated with hepatic artery perfusion chemotherapy. In addition, Morihara et al [23] found that LES also significantly improved Child-Pugh score in hepatocellular carcinoma patients at 4 and 12 weeks after radiofrequency ablation.

The improvement of nutritional status of LES for liver cancer patients is currently limited to the detection of several biochemical biomarkers and anthropometric measurements, which lacks a comprehensive understanding of metabolic changes. At the metabolic level, metabolomics is an important component of systems biology that allows the analysis of metabolic changes in the organism as a result of relevant factors. Pathologic changes in the liver affect the body's basal metabolism and have a more pronounced effect on the levels and types of small molecule metabolites, which provides a new perspective for applying metabolomic analysis to study the changes in metabolic patterns in patients with LES. In recent years, metabolomics has also been increasingly used in dietary intervention studies to discover new dietary biomarkers and to explore the metabolic changes associated with nutrients and dietary patterns, in order to evaluate the effects of dietary interventions on the disease of the organism. Tripodi et al [24] found that methionine supplementation in vitro could inhibit AMP-activated protein kinase and up-regulate the tricarboxylic acid cycle, through proteomics and metabolomics to inhibit hepatocellular carcinoma invasion. Rong et al [25] investigated the effect of antioxidant active substance corn oligopeptides on serum metabolism of hepatocellular carcinoma patients based on metabolomics combined with multivariate statistics. Initially, 16 differential metabolites were screened, and it was concluded that corn oligopeptides' protection of hepatic function was realized through nicotinic acid and nicotinamide metabolism and fatty acid metabolism pathways. However, it is not clear how LES affects the metabolic patterns of patients to improve nutritional status and liver function. As a result, metabolomics has the potential to make an important contribution to the study of the underlying mechanisms of LES to improve the nutritional status of patients and to the search for methods of nutritional support in malignant tumors.

Since, nutritional support with LES for hepatocellular carcinoma patients undergoing hepatectomy treatment has rarely been reported, and there are no clinical studies applying metabolomics approaches to explore the effects of LES on their metabolic patterns. In view of this background, the present study aimed to optimize the management of meal timing and frequency in patients with hepatocellular carcinoma undergoing hepatectomy using LES, with the aim of reducing patient complications and improving clinical outcomes, and to further study and explore the effects of LES on patients' metabolic patterns to

provide a theoretical basis for implementing effective nutritional strategies in clinical practice to promote patient recovery.

2. Research purpose

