3.2 Experimental Steps

The specific steps of the study are as follows:

Pre-procedure preparation:

According to the literature research, establish the form of patients' clinicopathological data that need to be collected, including basic information (age, gender, hospitalization number), pre-surgical laboratory examination (nutritional indexes, liver function, renal function, coagulation function, blood routine, tumor markers such as alpha-fetoprotein, etc.), surgical records (tumor location, size, number, intra-operative bleeding, etc.), post-surgical laboratory examination, tumor recurrence and treatment modality and patient survival, etc., as well as the establishment of a dietary matching table, respectively writing the dietary education content of the experimental group and the control group, in order to personalize the guidance of the patient's postoperative diet and the correct understanding of the importance of dietary therapy. A case questionnaire was set up for the enrolled patients, and the relevant data of the enrolled patients were recorded in the form.

Screening and Trial:

Patients who were admitted to the Department of Hepatobiliary Pancreatic Surgery of Drum Tower Hospital affiliated to Nanjing University School of Medicine, from February 2024 to January 2025 and met the enrollment criteria were selected for inclusion in this study. The grouping was not randomized and blinded, and all patients were enrolled according to their individual wishes and divided into a test group (53 cases) and a control group (53 cases). The purpose of the study, the content of the investigation, the principle of confidentiality were explained to the patients or their families at the time of their admission to the hospital to reduce the concerns of the respondents, and the subjects were included in the study after signing the informed consent form with their consent.

1. Treatment program:

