All patients were screened for nutritional risk using NRS 2002, nutritional assessment using PG-SGA, and malnutrition diagnosis using GLIM Malnutrition Assessment (Diagnosis) Criteria within 24h of admission. In accordance with the recommendations of ESPEN 2021 Practice Guidelines for Surgical Nutrition Therapy and CSPEN 2016 Guidelines for Perioperative Nutritional Support for Adults, the patients' daily target amount was set at 25-30 kcal/kg. In order to ensure the balanced dietary nutritional intake of the two groups, their standardized management was formulated as follows: ① Total calories: according to the patients' height, weight, age and activity Total calories: Calculate the daily intake according to the patient's height, weight, age and activity intensity, about 1200~2000 kcal. ② Carbohydrates: account for 60%~65% of the actual energy supply, calculate the actual supply of 180~325

g. The staple food is mainly cereals and potatoes. Protein: 1.2~1.5 g/kg/day according to the guideline, choose high quality protein, such as eggs, poultry, soybean products. ④Fat: account for 20% of the actual energy supply, calculate the actual supply of about 27~44 g. Distribute the energy of three meals as 30%, 40%, 30%. According to each patient's required intake, the corresponding nutritional program card is issued, and explained and emphasized at the time of admission and discharge, respectively. Patients could choose different food items on the cards according to their food preferences and actual situation. The experimental group was required to consume LES 1 h before bedtime, while the control group did not consume any food 1 h before bedtime.

Experimental group: patients were given additional meal (total calories 200-275kcal, protein 11.5g-18g, complex carbohydrates 25-55g) 1h before bedtime. the LES regimen was: ① whole protein type enteral nutrition; ② whey protein powder + bread or cookie. The addition of meals was carried out 1h before bedtime. The dietary regimen of the experimental group will be deducted from the corresponding late-evening snacks intake.

(1) Preoperative: ① Patients without nutritional risk: independent intake according to the issued diet program card. ② Patients with nutritional risk: daily oral whole-protein enteral nutrition on the basis of general diet after admission.

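### The synopsis control-group postoperative item ends by letting LES be continued, in conflict with the control no-food-before-bedtime rule and with the matching item in section 3.2

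*Combined protocol and SAP*

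**What the plan says.** **Synopsis, Treatment plan.** The general sentence requires LES in the test group, "while the control group did not have any food during the 1hour before bedtime". The control block opens with the same rule: "Control group: no more food 1h before bedtime". Item (2) Postoperative of that block sets the day-2 diet as semi-fluid food plus "daytime oral enteral nutrition of whole protein type. As the patient's voluntary intake meets 60% of the body's needs", and then closes with "the daytime oral enteral nutrition support can be gradually stopped and the LES regimen can be continued".

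The same closing words also end item (2) of the test group, so the location matters. The instance at issue follows a day-2 diet without LES and comes directly before the control item that begins "Discharge: the doctor will judge whether the patient needs to continue nutritional support".

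**Section 3.2, Treatment program.** The general sentence again requires LES in the experimental group, "while the control group did not consume any food 1 h before bedtime", and the control heading repeats the rule. Control item (2) follows the same sequence as in the synopsis, but it stops once enteral nutrition is tapered and does not mention LES. In this section only the experimental group's item has the clause about continuing LES.

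**Section 5.1, item 3) Interventions.** The control group is again described as taking no food in the hour before bedtime.

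**The concern.** One item in the operative treatment plan says that LES may go on in the control group. The heading above it, and every statement of the control bedtime rule elsewhere, says that controls do not eat in that hour. Staff working from the synopsis and staff working from section 3.2 would hold different instructions for the same patients.

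This matters more than an ordinary slip because bedtime LES is the one planned difference between the groups. The study is open and patients join a group by their own wish, so the written instructions are what keep the two regimens apart. If some controls took LES after surgery, the albumin comparison would no longer be the planned contrast for those patients.

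**Working it through.** The check is textual. No sample size, alpha or power figure depends on this clause, so there is no figure of the plan to reproduce.

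**1. Control postoperative item, side by side**

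| Element | Synopsis, control (2) | Section 3.2, control (2) |
|---|---|---|
| LES in the day-2 diet | no | no |
| Trigger | voluntary intake at 60% of needs | voluntary intake at 60% of needs |
| Enteral nutrition | tapered | tapered |
| LES clause at the end | yes | no |

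The two items differ in substance only in the last row.

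**2. Statements of the control no-food rule**

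- Synopsis: general sentence and control heading = 2
- Section 3.2: general sentence and control heading = 2
- Section 5.1 item 3 = 1
- Total: 2 + 2 + 1 = 5

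One clause therefore stands against five statements of the rule and one matching item.

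**3. Would section 4.4 item 5 catch the exposure?** That item removes controls with more than 7 additional bedtime meals. Assume, as the most exposure the clause could allow before the first postoperative albumin value, that a control took LES every evening from postoperative day 2 (the first day on which LES appears in the test-group text) and that the day-6 sample was drawn before that evening. The evenings are days 2, 3, 4 and 5, which is 5 − 2 + 1 = 4 meals. Since 4 is not more than 7, the patient stays in. The clause takes effect only when voluntary intake reaches 60% of needs, so the number could be lower.

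**4. Which albumin values are touched?** Albumin is taken on admission day 1, on postoperative day 6, and at 1, 3 and 6 months (section 6.2). Exposure confined to the in-hospital postoperative period bears mainly on day 6.

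**5. Would it be seen?** Section 6.1 has daily intake and its timing recorded in the perioperative period. Bedtime meals in controls would show in those data.

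**The case against.** The best reply is that the clause would do little in practice. It speaks of continuing LES, yet no control item starts LES, and a snack composition is given for the test group only. The control block carries the no-food rule as its heading. The word-for-word match with the test-group ending suggests text carried over from there, although that is an inference. Staff may well read past it. This lowers the likelihood of harm and stands as a limit on severity. It does not remove the conflict, because the clause sits in the treatment plan itself and gives an instruction about the study intervention.

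Four stronger readings are tempting, and the protocol does not support them.

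- *The clause also contradicts the control discharge rule.* That rule, under which "his/her supplementation must be completed before 1h before bedtime", belongs to item (3), a later phase. A postoperative clause does not directly contradict it.
- *Controls would be removed for following the printed text.* More than 7 meals means at least 8. With LES nightly from day 2, the eighth falls on day 2 + 7 = 9, or later if the 60% trigger comes later. No expected length of stay is given, so it is unknown whether any control could reach that number in hospital.
- *The albumin comparison is diluted.* No crossover rate is given, and the values at 1, 3 and 6 months lie well beyond a few in-hospital evenings. The tolerance of up to 7 control bedtime meals comes from section 4.4 and exists with or without this clause.
- *The clause in the control block is the mistaken text.* The documents show that the statements disagree. Which dietary instruction stands is a clinical decision.

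**Conclusion.** The point holds as a conflict of text: the LES clause in the synopsis control item cannot stand together with the five statements of the control no-food rule, and it is absent from the matching item in section 3.2. Confidence is high for that conflict and does not extend to any effect on the results.

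Read literally, the clause could let controls receive LES in hospital after surgery, with up to 4 meals before the day-6 albumin sample under the assumptions stated in the working. Section 4.4 item 5 would leave such patients in. The size of any effect on albumin cannot be estimated from the documents. The intake record would reveal the exposure but not prevent it. This should be fixed because it concerns the intervention itself and is cheap to put right; it is not evidence that the comparison has been compromised.

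**What to change.** Reconcile item (2) Postoperative of the control block in the synopsis with the control text in sections 3.2 and 5.1, so that one statement governs the control group. The clinical team decides which statement stands.

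Then check the patient-facing material against the agreed statement: the nutritional cards described in the synopsis and section 3.2, and the education text planned in section 3.2 under "respectively writing the dietary education content of the experimental group and the control group".

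The cost is a wording correction to the protocol and a check of the cards and education text. It needs no extra patients or procedures and changes no sample size, alpha or power.
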